**Safety Analysis:**

Adverse events will be coded to system organ class and preferred terms using the Medical Dictionary for Regulatory Activities (MedDRA, Version 20 or higher).

Frequency and percentage of subjects reporting treatment-emergent adverse events (TEAEs) will be tabulated for each treatment by preferred terms and further by severity and relationship to study device. In summaries of severity and relationship, subjects reporting more than one event in a treatment arm that are mapped to the same preferred term will be counted only once in that treatment arm under the strongest severity and relationship, respectively. In addition, visual

related TEAEs will be summarized separately for each treatment by preferred term.  
Safety analyses will be conducted using the ITT population.

## 2 SCHEDULE OF ACTIVITIES

Visit Number (Month)	Visit 1 (Week 0)	Phone Contacts	Visit 2 (Mo 1)	Phone Contacts a	Visit 3 (Mo 2)	Visit 4 (Mo 3)	Phone Contacts	Visit 5 (Mo 6) End of Study/Early Termination	Unsched Visit
Scheduled Day(s)	Day 1	Day 3 & Day 14	Day 28	Day 33 & Day 44	Day 56	Day 84	Day 112 & Day 140	Day 168 b	
Scheduling Window	none	± 2 days	± 2 days	± 2 days	± 4 days	± 4 days	± 4 days	± 7 days	
Informed consent	X								
Medical history/ demographics	X								
Abbreviated Physical examination (including vital signs)	X								
Vision evaluations (Snellen visual acuity, confrontational visual fields, ocular motility) d	X		X		X	X	X	X	X c
Prior/Concomitant Medication/ Treatment	X	X	X	X	X	X	X	X	X
Inclusion/exclusion criteria review	X								
Urine pregnancy test e	X								
Fitzpatrick Skin Type	X								
Lip Fullness Grading Scale (LFGS) (Overall, upper lip and lower lip)	X		X		X	X		X	X c
Perioral lines at rest severity scale (POL) (Overall, upper lip and lower lip)	X		X		X	X		X	X c
Randomization	X								
Treatment with study device	X		X a						
Investigator Ease of Use Assessment	X		X a						
Evaluation for touch-up			X						
Patient GAI (pGAI)			X		X	X		X	X c
Swelling Assessment			X		X	X		X	X c
Investigator GAI (iGAI)			X		X	X		X	X c
Subject Satisfaction with Lips			X		X	X		X	X c
Lip Function (prior to injections)	X		X		X	X		X	X c
Lip Sensation (prior to injections)	X		X		X	X		X	X c
Lip Texture (prior to injections)	X		X		X	X		X	X c
Lip Firmness (prior to injections)	X		X		X	X		X	X c

Lip Symmetry (prior to injections)	X		X		X	X		X	X c
Lip Movement/Function	X		X		X	X		X	X c
Adverse event assessment	X	X	X	X	X	X	X	X	X
Treatment question								X	
Subject Diary	Dispense		Collect/ dispense f		Collect f				

Note: The timing of each visit is relative to Day 1, which is defined as the day the subject is randomized and first treated.

- a. For subjects who have touch-up treatment at Visit 2
- b. All subjects will receive a follow-up phone call at 12 months after first treatment.
- c. If/as needed
- d. performed prior to any treatment and repeated 30 minutes following any treatment and all follow-up visits.
- e. For women of childbearing potential, to be completed prior to enrollment.
- f. Dispense/collect diary only if touch up is performed

**4 LIST OF ABBREVIATIONS AND DEFINITIONS OF TERMS**

Term	Definition
AE	adverse event
CFR	Code of Federal Regulations
CI	confidence interval
CRA	Clinical Research Associate
CRF	case report form, paper or electronic
DCF	data correction form
EOS	end of study
FDA	Food and Drug Administration
GCP	Good Clinical Practice
ICF	informed consent form
ICH	International Council for Harmonisation
iGAI	Investigator Global Aesthetic Improvement
IRB	Institutional Review Board
ITT	intent-to-treat
IUD	intrauterine device
LFGS	Lip Fullness Grading Scale
MedDRA	Medical Dictionary for Regulatory Activities
mITT	modified intent-to-treat
NSAID	nonsteroidal anti-inflammatory drug
OTC	over-the-counter
pGAI	Patient Global Aesthetic Improvement
PI	principal investigator
POL	perioral lines at rest
PP	per-protocol
SAE	serious adverse event
SAR	suspected adverse reaction
TEAE	treatment-emergent adverse event
VAS	visual analog scale

## **5 INTRODUCTION**

### **5.1 Background**

PN40082 is a stabilized hyaluronic acid dermal filler with lidocaine. Restylane Silk Injectable Gel with 0.3% lidocaine (hereafter referred to as Restylane Silk) is a stabilized hyaluronic acid dermal filler with lidocaine that is commercially available for submucosal implantation for lip augmentation and dermal implantation for correction of perioral rhytids in adults over the age of 21 years. The purpose of this study is to compare the efficacy and safety of PN40082 and Restylane Silk for lip augmentation.

### **5.2 Rationale for the Study and Study Design**

To be enrolled in the study subjects who have a Lip Fullness Grading Scale (LFGS) score of very thin, thin, or moderately thick must be seeking at least a 1-point improvement in their overall LFGS score and subjects who have an LFGS score of thick or full must be seeking treatment to the vermilion body of 1 for both lips. Subjects will be randomized 1:1 to treatment with either PN40082 or Restylane Silk. All subjects will be followed for efficacy and safety for 6 months. All subjects will be evaluated for retreatment and undergo consent procedure for the subsequent open-label retreatment protocol.

## **6 STUDY OBJECTIVES**

To compare the safety and efficacy profile of PN40082 versus Restylane Silk for lip augmentation.

## **7 INVESTIGATIONAL PLAN**

### **7.1 Overall Study Design**

This is a double-blind, randomized, controlled, multicenter clinical study of subjects seeking lip augmentation. Subjects meeting inclusion/exclusion criteria will be randomized 1:1 to treatment with either PN40082 or Restylane Silk. The Evaluating Investigator will be blinded to the treatment. Injections of the study device will be performed by an unblinded Treating Investigator.

At each visit, the blinded Evaluating Investigator evaluations and subject evaluations of the treated areas will be performed and recorded. Visits and telephone contacts will occur at:

Visit 1 / Week 0 (Day 1) – baseline and treatment

-Day 3 ( $\pm 2$  days) - Safety follow-up telephone call

-Day 14 ( $\pm 2$  days) – Safety follow-up telephone call

Visit 2 / Day 28 ( $\pm 2$  days) / Month 1 – interim visit (touch-up if necessary)

-Day 33 ( $\pm 2$  days) – Safety follow-up telephone call (for subjects with touch-up treatment)

-Day 44 ( $\pm 2$  days) – Safety follow-up telephone call (for subjects with touch-up treatment)

Visit 3 / Day 56 ( $\pm 4$  days) / Month 2 – interim visit

Visit 4 / Day 84 ( $\pm 4$  days) / Month 3 – interim visit

-Day 112 ( $\pm 4$  days) / Month 4 – Safety follow-up telephone call

-Day 140 ( $\pm 4$  days) / Month 5 – Safety follow-up telephone call

Visit 5 / Day 168 ( $\pm 7$  days) / Month 6 – End of Study (EOS) Visit. All subjects will be evaluated for retreatment and undergo the consent procedure for the subsequent open-label retreatment protocol.

Efficacy valuations include:

Lip Fullness Grading Scale (LFGS) (Overall lip fullness considering both lips together, fullness of the upper lip and fullness of the lower lip)

Perioral lines at rest severity scale (POL) (Overall perioral lines at rest severity considering both lips together, perioral lines at rest severity of the upper lip and perioral lines at rest severity of the lower lip)

Patient Global Aesthetic Improvement (pGAI)

Investigator Global Aesthetic Improvement (iGAI)

Safety will be assessed by monitoring adverse events (AEs) at all study visits. Adverse Events of Special Interest, any changes in vision and any events attributable to an embolic or ischemic cause (i.e., skin infarction) will be monitored. Other Safety evaluations include lip function, lip sensation, lip texture, lip firmness, lip symmetry, and lip movement/function. Other evaluations include Investigator Ease of Use Assessment, Swelling Assessment, and Subject Satisfaction with Lips Assessment.

## **7.2 Beginning and End of Study**

A subject is considered to be enrolled in the study when he/she has provided written informed consent and has been randomized to treatment.

A subject is considered to have completed the study after he/she has completed Visit 5/ Month 6.

A subject is considered to have withdrawn after he/she has withdrawn consent or has been withdrawn under the conditions specified in Section 7.3.3.

A subject is considered to have been lost to follow-up if he/she cannot be contacted by the investigator. The investigator will document efforts to attempt to reach the subject at least twice by telephone and will send a certified letter before considering the subject lost to follow-up. The end of participation for a subject lost to follow-up is documented as the date of the certified letter.

Each subject will be monitored for the occurrence of AEs, including serious adverse events (SAEs), immediately after treatment initiation. Each subject will be followed for safety monitoring until he/she is discharged from the study.

Follow-up procedures related to pregnancy, AEs, or SAEs may continue beyond the end of the study.

Each subject will participate in the study for approximately 6 months. After determination of eligibility at Visit 1/Day 1, each subject will be treated with PN40082 or Restylane Silk.

It is anticipated that the duration of this study will be 20 months from the first subject signing the ICF to the Month 6 EOS visit last subject.

At the end of study visit the subjects who have completed Visit 5/Month 6 within window will be invited to participate in an open-label retreatment study, PRO 2018-03.

## **7.3 Study Population**

Approximately 158 healthy males and females over 21 years of age seeking lip augmentation will be selected to participate in the study.

### **7.3.1 Inclusion Criteria**

Subjects must meet all of the following criteria to be eligible for the study:

1. Men or non-pregnant or non-breastfeeding women over 21 years of age
2. If female and of childbearing potential, a negative urine pregnancy test at Baseline (Day 1) and the subject agrees to use adequate contraception during the study period

3. Has an overall score of very thin or thin on the LFGS, as agreed upon by the Treating and Evaluating Investigators, and desires at least a 1-point improvement in overall LFGS score; OR  
Has a Fitzpatrick skin phototype IV, V or VI and has an LFGS score of thick or full, as agreed upon by the Treating and Evaluating Investigators, and desires treatment to the vermilion body of 1 or both lips
4. Willing to give written informed consent

### 7.3.2 Exclusion Criteria

Subjects who meet any of the following criteria will be excluded from the study:

1. Women who are pregnant, lactating, or planning a pregnancy
2. History of allergy, anaphylaxis or hypersensitivity to injectable hyaluronic acid products, local anesthetics of the amide type such as lidocaine, or to latex, or is planning to undergo desensitization therapy during the study
3. Has lip tattoos, piercings, facial hair, or scars that would interfere with visualization of the lips and perioral area for the effectiveness assessments
4. Has abnormal lip function, with inability to effectively sip water through a straw
5. Has abnormal lip sensation, with inability to feel a 0.4G monofilament or a cotton wisp at any site on the lip
6. Has moderate or severe abnormal lip asymmetry
7. Has any mass formation on the lip
8. Has dentures or any device covering all or part of the upper palate, and/or severe malocclusion or dentofacial or maxillofacial deformities as judged by the Treating Investigator. Subjects planning to undergo extensive dental procedures such as dental implants, multiple tooth extractions, or oral surgery should not participate. Minor dental procedures such as teeth cleaning and repair of caries are not exclusionary
9. Has undergone facial plastic surgery or received permanent facial implants (e.g., polymethylmethacrylate, silicone, polytetrafluoroethylene, polyacrylamide, lifting threads) anywhere in the face or neck, or is planning to be implanted with any of these products during the study
10. Has undergone semi-permanent dermal filler treatment (e.g., calcium hydroxylapatite, poly-L-lactic acid) in the lower face (below the orbital rim) within 12 months before enrollment or is planning to undergo such treatment during the study
11. Has undergone facial tissue augmentation with fat injections, botulinum toxin injections in the lower face (below the orbital rim), mesotherapy, or cosmetic procedures in the face or neck (e.g., face-lift, laser, photo-modulation, intense pulsed light, radio frequency, dermabrasion, moderate or greater depth chemical peel, microneedling, or other ablative procedures) within 9 months before enrollment or is planning to undergo any of these procedures during the study
12. Has used ANY lip filling agents within 12 months of study enrollment (hyaluronic acid products, collagen-based products, etc.)
13. Has used any lip plumping products or devices within 10 days before enrollment or is planning to use such products during the study
14. Has begun using any over-the-counter (OTC) or prescription oral or topical anti-wrinkle products for the lips or around the mouth within 90 days before enrollment or is planning to begin using

such products during the study (Subjects who have been on a stable regimen of such products for at least 90 days are eligible for the study and must continue their regimen throughout the study.)

15. Is on an ongoing regimen of anticoagulation therapy (e.g., warfarin), thrombolytics, or inhibitors of platelet aggregation or nonsteroidal anti-inflammatory drugs (NSAIDs, e.g., aspirin, ibuprofen) or other substances known to increase coagulation time (e.g., herbal supplements with garlic or ginkgo) within 10 days of undergoing study device injections. Subjects who will withhold such therapy for 10 days before AND after any injection session may participate
16. Has a history or presence of bleeding disorders
17. Has used systemic corticosteroids or immunosuppressive medications within 30 days prior to treatment
18. Is on a concurrent regimen of lidocaine or structurally related local anesthetics (e.g., bupivacaine)
19. Has an active inflammation (skin eruptions such as cysts, pimples, rashes, or hives), infection, cancerous or precancerous lesion, or unhealed wound on the face
20. Has a history of known susceptibility to keloid formation or hypertrophic scars
21. Has porphyria
22. Has active herpes labialis lesions at the time of injections. Subjects with a history of herpes labialis who have had four (4) or more outbreaks in the 12 months prior to enrollment are also excluded even in the absence of lesions at the baseline visit
23. Has impaired cardiac conduction, severely impaired hepatic function, or severe renal dysfunction that, in the opinion of the investigator, would place them at risk of associated complications from these illnesses during the course of the study
24. Has any uncontrolled disease, i.e., a condition that has not been appropriately diagnosed, evaluated, and received medically appropriate treatment or care
25. Has severe cardiovascular disease; examples include but are not limited to New York Heart Association heart failure classification III or IV, unstable angina, and internal pacemakers. Potential subjects with other significant cardiovascular diseases should be discussed with the Medical Monitor before enrolling

### 7.3.3 Subject Withdrawal Criteria

A subject may withdraw from the study at any time for any reason.

A subject will be withdrawn from the study if his/her safety or well-being is determined to be at risk. Withdrawal will be made at the discretion of the investigator or at the subject's request.

A subject must withdraw from the study for any of the following reasons:

- The subject or legal representative withdraws consent
- The subject's study device assignment is unblinded
- There is a significant protocol violation as determined by the Sponsor or medical monitor.

A subject may be withdrawn from the study for any of the following reasons:

- Lost to follow-up
- Investigator discretion

Withdrawal is permanent; after a subject has been withdrawn, he/she will not be allowed to enroll again.

If a subject is withdrawn from the study for any reason, the EOS or Early Termination procedures (Visit 5/Month 6) should be completed and any outstanding data and subject diaries should be collected. Data, including the date and primary reason for withdrawal, must be documented on the EOS case report form (CRF) and source document.

If a subject withdraws from the study at any time due to an AE, the reason for withdrawal, the nature of the AE, and its clinical course must be fully documented. The investigator must strive to follow the subject until the AE has resolved, become clinically insignificant, is stabilized, or the subject is lost to follow-up. For any SAE, follow the procedures provided in Section 7.9.7.

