### **7.9.7 Reporting Safety Observations**

Any SAE, whether deemed device-related or not, must be reported to the Sponsor or designee by telephone, email or fax as soon as possible after the investigator or coordinator has become aware of its

occurrence. The investigator/coordinator must complete a Serious Adverse Event (SAE) Form and email or fax it to the Sponsor or designee along with the subject's Adverse Events Log and Concomitant Medications Log within 24 hours of notification of the event. The Sponsor will notify the FDA of device-related SAEs.

Designee and Sponsor contact details:

[REDACTED]	[REDACTED]	[REDACTED]
[REDACTED]	[REDACTED]	Prollenium Medical Technologies, Inc. [REDACTED]

The investigator must be prepared to supply the medical monitor with the following information:

1. Investigator name and site number
2. Protocol number
3. Subject ID (screening/randomization) number
4. Subject initials and date of birth
5. Subject demographics
6. Clinical event
  - a. description
  - b. date of onset
  - c. severity
  - d. treatment (including hospitalization)
  - e. relationship to study device
  - f. action taken regarding study device
  - g. if the AE was fatal or life-threatening:
    - i. cause of death (whether or not the death was related to study device)
    - ii. autopsy findings (if available)

The Sponsor must submit a written summary of the clinical course of any life-threatening SAE and related subject information to the FDA within 7 days. Serious and unexpected AEs that are not life-threatening must be reported to the FDA within 15 calendar days. Any serious and unexpected AE

(including all deaths) must also be reported to the Institutional Review Board (IRB) by the investigator according to IRB reporting requirements and documentation of this report sent to the Sponsor or designee.

The investigator must provide a follow-up written report within 5 calendar days of reporting the event to the medical monitor. The written report must contain a full description of the event and any sequelae. Subjects who have had an SAE must be followed clinically until all parameters (including laboratory) have either returned to normal or are stabilized.

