##### **7.9.10.2 Unblinding Treatment for a Subject During the Study**

Unblinding by the investigator should occur only in the event of an AE or SAE for which it is necessary to know the study treatment to determine an appropriate course of therapy for the subject. In the event of an emergency that requires breaking of the study blind, the Investigator can unblind the subject without prior contact with the Medical Monitor although the Investigator will immediately notify the Medical Monitor accompanied by a written explanation of the reason why the blind was broken. In the event of an emergency that requires breaking of the study blind, the randomization code will be maintained by each unblinded Treating Investigator that can be opened to reveal the study device to the applicable staff. In the event the unblinded Treating Investigator is not available, the site should designate another unblinded staff member not involved in the study conduct to access the randomization code for that

subject. Note this can be done WITHOUT informing the blinded Evaluating Investigator and thus maintaining the study blind. If unblinding occurs, the subject must be withdrawn from the study.

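### Mandatory study withdrawal after unblinding or a significant violation ends scheduled follow-up of subjects whose device is already implanted

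*Protocol*

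**What the plan says.** Protocol 7.3.3 lists the grounds on which a subject must leave the study. Two matter here: "The subject's study device assignment is unblinded" and "There is a significant protocol violation as determined by the Sponsor or medical monitor". Withdrawal is permanent, and under 7.3.4 the subject is not replaced.

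Protocol 7.9.10.2 repeats the first ground: "If unblinding occurs, the subject must be withdrawn from the study". It also limits when the code may be broken: "Unblinding by the investigator should occur only in the event of an AE or SAE", and then only if care depends on knowing the product. It adds: "Note this can be done WITHOUT informing the blinded Evaluating Investigator and thus maintaining the study blind".

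Some data collection survives withdrawal. Section 7.3.3 says: "If a subject is withdrawn from the study for any reason, the EOS or Early Termination procedures (Visit 5/Month 6) should be completed". For a subject who leaves because of an AE it adds: "The investigator must strive to follow the subject until the AE has resolved, become clinically insignificant, is stabilized". Section 7.9.7 says: "Subjects who have had an SAE must be followed clinically until all parameters (including laboratory) have either returned to normal or are stabilized". Section 7.9.5 also calls for repeated assessment of SAEs and of AEs that force withdrawal, but it ends general safety monitoring at discharge from the study.

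On the analysis side, SAP Section 4 keeps every treated subject in the As-Treated safety set. Per-protocol (PP) is the primary efficacy set and requires an in-window Visit 5. mITT requires eligibility and treatment, not completion. SAP 5.2 assigns a termination-visit score to the nearest scheduled visit and then multiply imputes missing overall LFGS, for mITT only.

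**The concern.** The device is injected on Day 1, with at most one optional touch-up at Visit 2. After that there is no study treatment to stop, and withdrawal ends only the observation of an implant that stays in the subject.

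The subjects concerned are not a random sample. Those withdrawn for unblinding had an adverse event by rule; the others had a violation that the sponsor or medical monitor judged significant. Ending their schedule makes missing data depend on events in the trial.

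Neither ground clearly needs this. The primary endpoint is the blinded evaluator's rating, and the protocol itself says that the evaluator's blind can survive a code break. Significant violations are already handled in SAP Section 4 by exclusion from PP, so withdrawal adds no analytic protection.

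At stake are systematic capture of later-onset events and the completeness of the supportive mITT analysis.

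**Working it through.** **1. What a subject loses, by time of withdrawal.** Visit days and calls come from the Protocol Section 2 schedule; mapping to the nearest visit comes from SAP 5.2. The midpoint between Visits 2 and 3 is (28 + 56)/2 = Day 42.

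| Withdrawn on | Scheduled contacts replaced by one termination visit | Days to Day 168 | Month 2 overall LFGS in mITT | In PP? |
|---|---|---|---|---|
| Day 20 | Visits 2–5; calls Days 112, 140 | 148 | imputed | no |
| Day 33, after touch-up | Visits 3–5; calls Days 44, 112, 140 | 135 | imputed (termination score is nearest Visit 2) | no |
| Day 50 | Visits 3–5; calls Days 112, 140 | 118 | termination score stands in for Visit 3 | no |
| Day 70 | Visits 4–5; calls Days 112, 140 | 98 | measured score kept | no |

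The last column is always no because none of these subjects completes Visit 5 in its window.

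**2. Later-onset events.** The Restylane Silk labelling (Warnings) gives delayed onset of injection site reactions at 21 to 142 days after treatment. Counted from Day 1, that is Day 22 to Day 143. The schedule has five contacts in that span (Visits 2, 3 and 4; calls at Days 112 and 140), or seven with the two touch-up calls. A subject withdrawn on Day 20 has none of them. The labelling also reports 19 subjects with lip events starting more than 3 weeks after injection, none serious. The SAE follow-up duty would therefore not reach such events, and AE follow-up covers events already present at withdrawal. The PN40082 instructions give no comparable range.

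**3. How many subjects.** The documents give no rate. Assuming 1% to 3%: 158 × 0.01 = 1.6 and 158 × 0.03 = 4.7, so about 2 to 5 subjects. With 218 subjects treated in the labelling's study, 19/218 = 8.7%; applied to 2 to 5 subjects, this gives about 0.2 to 0.4 subjects with a delayed lip event. Subjects who already had an AE could differ.

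**4. Power.** Protocol 8.5 uses SD 0.85, margin 0.50 and 90% power; the 95% CI in 8.2 gives one-sided 0.025.
- Normal formula: n per arm = 2 × [0.85 × (1.95996 + 1.28155)/0.50]² = 60.7, so 61. The t-based version gives 62; the plan has 63.
- 126/0.80 = 157.5, so 158, as stated.
- Expected PP size: 158 × 0.80 = 126.4.

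| Extra forced withdrawals (assumed) | PP subjects | t-based power |
|---|---|---|
| 0 | 126 | 90.7% |
| 3 | 123 | 90.0% |
| 5 | 121 | 89.5% |
| 10 | 116 | 88.2% |

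**5. Imputation.** The model in SAP 5.2 contains treatment, site, age, gender, race, Fitzpatrick type and earlier LFGS. It has no term for AE status or withdrawal reason. Suppose a fraction f of one arm is imputed as if like the rest, while its true mean change is d grades lower. That arm's mean is then overstated by f × d. For f = 5% (79 × 0.05, about 4 subjects) and d = 0.5 to 2, the shift is 0.025 to 0.10 grade, or 5% to 20% of the 0.50 margin. Both f and d are assumptions, and earlier LFGS in the model would absorb part of the shift. This is on the mean scale; SAP 5.5.1 uses a Hodges-Lehmann interval with a limit of -1.0, a discrepancy that is a separate matter.

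Only overall LFGS is imputed. Month 3 perioral line scores not yet taken are simply missing.

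**The case against.** The strongest reply is that little is really removed.
- Every event before withdrawal is analysed in the As-Treated set, and withdrawal for any reason calls for the full Visit 5 procedures.
- An AE that led to unblinding plausibly falls under 7.9.5 as one that forced withdrawal, so it would be followed to an outcome. SAEs are followed too, and vision and embolic events have their own reporting route in 7.9.3.4.
- A Month 2 score taken before withdrawal stays in mITT.

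All of this stands. It rules out the reading that the rule removes the most informative safety and Month 2 data. What it does not cover is events that begin after withdrawal, or a non-serious AE in a subject withdrawn for a violation, whom the 7.3.3 duty does not clearly reach.

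Three further objections also stand in part.
- Not every important AE leads to unblinding. The Treating Investigator already knows the product, and the first-aid steps in Appendix 1 are the same for both. A reader might infer that exactly the subjects with important AEs are lost; the documents do not show that.
- The protocol says the evaluator's blind can be kept, not that it will be. If the subject learns the assignment, later pGAI and satisfaction scores are no longer blinded.
- A withdrawal before Visit 2 also ends access to the touch-up, so it is not strictly true that only follow-up is lost.

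Finally, PP is primary and is not imputed, so the efficacy gain from a change lies mainly in the supportive mITT analysis.

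**Conclusion.** The point holds in a limited form. The two mandatory withdrawal rules end scheduled follow-up of already implanted subjects who are selected by a safety event or violation. They leave a termination visit and event-specific follow-up. The cost is less systematic capture of later-onset events, and later overall LFGS in mITT that is imputed without reference to the reason it is missing.

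The effect is probably small. The number affected is unknown, the 1% to 3% range is an assumption, and the delayed-onset figures come from the comparator's labelling. Power is not materially affected: even ten extra losses cost about 2.5 points. The case rests on who is lost and how cheaply they could be kept, not on any threat to the primary conclusion.

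**What to change.** In Protocol 7.3.3 and 7.9.10.2, replace compulsory study withdrawal for these two reasons with wording such as: *excluded from PP where the PP definition requires; continues all scheduled follow-up assessments unless consent is withdrawn; remains in the As-Treated set, and in mITT if the inclusion and exclusion criteria were met*. The last condition is needed because mITT already excludes subjects who failed eligibility.

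Alongside this:
- Keep the evaluator blinded after a code break, and record whether the evaluator or the subject learned the assignment, so that later LFGS, pGAI and satisfaction scores can be flagged.
- State in the SAP whether unblinding alone counts as a significant violation for PP. If it does, this change leaves the primary result untouched.
- State separately whether the Visit 2 touch-up remains available to such a subject. No rule is proposed here.

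The cost is a wording amendment; the visits and calls are already scheduled for every subject. The downside is that a few later ratings may be unblinded and need flagging or a sensitivity analysis.
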